10.1. Definitions

The following definitions will apply to the reporting of adverse events:

1. Serious Adverse Event: Any adverse experience occurring at any dose that is fatal or life threatening; requires in-patient hospitalization or prolongation of an existing hospitalization; is a persistent significant disability/incapacity; is a congenital anomaly or birth defect; or is an important medical event that may not result in death, be life-threatening, or require hospitalization but, based upon appropriate medical judgment, may jeopardize the subject and may require medical or surgical intervention to prevent one of the outcomes listed above.
2. Unexpected Adverse Event: Any adverse experience that is not identified in nature, severity, or frequency in the Investigator's Brochure for NTZ.
3. Severity of adverse events will be assessed by the Investigator using the Toxicity Grading Scale Tables provided in [Appendix II](#) (derived and adapted from "Guidance for Industry: Toxicity Grading Scale for Healthy Adult and Adolescent Volunteers Enrolled in Preventive Vaccine Clinical Trials", US Dept. of HHS, FDA, CDER, September 2007 and the National Institutes of Health, National Cancer Institute Common Terminology Criteria for Adverse Events (CTCAE) version 4.0).
4. Causality (relationship to treatment) will be assessed as follows:
 - *Definitely Related*: The adverse event is clearly related to the investigational agent(s) or research intervention: the adverse event has a temporal relationship to the administration of the investigational agent(s) or research intervention, follows a known pattern of response, and no alternative cause is present.
 - *Probably Related*: The adverse event is likely related to the investigational agent(s) or intervention: the adverse event has a temporal relationship to the administration of the investigational agent(s) or research intervention, follows a known or suspected pattern of response, but an alternative cause may be present.
 - *Possibly Related*: There is a reasonable possibility that the event may have been caused by or is linked in a significant way to the research; the adverse event has a temporal relationship to the administration of the investigational agent(s) or research intervention, follows a suspected pattern of response, but an alternative cause is present.
 - *Unrelated (or Not Related)*: The adverse event is clearly NOT related to the investigational agent(s) or intervention: the adverse event has no temporal relationship to the administration of the investigational agent(s) or research intervention, follows no known or suspected pattern of response, and an alternative cause is present.

Under double-blind treatment conditions, it should be assumed that all subjects are taking the test drug.

10.2. Clinical Adverse Events

At the time of each return visit, the subject will be questioned regarding the occurrence and nature of any adverse events. All events must be recorded in the subjects' medical records and in the EDC system. Any subject affected will be examined by the Investigator as deemed necessary to ascertain the course of the event and any residual effects.

All moderate and severe adverse events will be reviewed by the Principal Investigator who will determine using his/her best clinical judgment whether they warrant the subject to be discontinued from the study. The Sponsor will be notified immediately if a subject is discontinued from the study. For all adverse events that require the subject to be discontinued from the study, relevant clinical assessments and laboratory tests will be repeated as clinically indicated until final resolution or stabilization of the event(s).

All subjects will be instructed to contact the Investigator, Investigator's assistants, or clinical personnel should the subject have any serious adverse experiences. Serious adverse events (SAEs), including death regardless of the cause, must be reported to the Sponsor immediately (within 24 hours of the initial report).

A serious event requiring immediate notification by telephone is an event that:

- results in death
- is life threatening
- requires inpatient hospitalization or prolongation of an existing hospitalization
- is a persistent or significant disability/incapacity
- is a congenital anomaly/birth defect
- an important medical event that may not result in death, be life-threatening, or require hospitalization but, based upon appropriate medical judgment, may jeopardize the subject and may require medical or surgical intervention to prevent one of the outcomes listed above.

An overdose is defined as any intentional or unintentional consumption of the drug by any route that exceeds the highest dose stated in the Investigator's Brochure or in an investigational protocol, whichever dose is larger. Overdoses without an associated adverse event should be recorded, but not reported as an adverse event.

10.3. Reporting Requirement

The Principal Investigator is required to notify The Romark Institute for Medical Research (Sponsor) immediately of any unexpected, fatal, or life-threatening experience and all unusual, alarming, or serious reactions to medication regardless of any opinions as to the cause/effect relationship. All SAEs will also be reported to the IRB. Adverse events should be reported to:

The Romark Institute for Medical Research
Medical Affairs
[REDACTED]

Tel: [REDACTED]
[REDACTED]

10.4. Medication Modification/Withdrawal Due to an Adverse Event

No dose adjustment is permitted during the 5-day treatment period. If a severe adverse reaction develops during therapy, the study medication should be discontinued, and the subject should be withdrawn from the study.

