5.9. Study Discontinuation

Rules for discontinuation of a subject or for discontinuing the study are provided in section [11.2](#). All subjects discontinued from the study before Day 7 will be evaluated at study discontinuation using the procedures described above for Day 7. All subjects discontinued from the study after Day 7 will be evaluated at study discontinuation using the procedures described above for Day 22.

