9.5. Subject Compliance

Subject compliance with the protocol will be checked by the Investigator and recorded in the EDC system at each visit.

Subjects will be considered non-compliant (major protocol violation) if they have missed more than two doses of the study medication during the first three days of the study. Non-compliance will not be cause for discontinuation of subject participation in the study.

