10. ADVERSE EVENTS

The term “adverse event” is defined for purposes of this study as any unwanted physical, psychological or behavioral change experienced by a subject during the course of the study and after taking the first dose of study medication regardless of its severity or relation to the study. Adverse events may include symptoms, signs, unexpected worsening of pre-existing conditions, clinically significant changes in laboratory values, diseases and syndromes, and significant and unexpected failures of pharmacological action of other medications. Symptoms of colds due to EV/RV infection (cough, sore throat, nasal obstruction, fatigue, headache, myalgia, feverishness) and complications of colds will not be reported as adverse events.

Adverse events will be recorded on the appropriate EDC forms throughout the study, and the severity of each adverse event will be graded on a four-point scale: mild, moderate, severe, or life-threatening ([See Appendix II](#)). The duration of the adverse event and relationship to the study drug will also be recorded. All adverse events must be followed until their resolution or stabilization even beyond the planned study period.

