11. DISCONTINUATION

11.1. Study Discontinuation

The study may be discontinued under the following circumstances:

1. The Sponsor reserves the right to discontinue the study at any time.
2. Adverse event listings will be produced for safety monitoring at least once every two weeks during recruitment. The data will be tested to determine if there are greater than 5% of the subjects who have had \geq Grade 3 adverse events considered by the Investigator to be possibly, probably or definitely related to the study drug (defined by the Toxicity Grading Scale Tables provided in [Appendix II](#)).

If greater than 5% of the subjects have at least one Grade 3 or Grade 4 adverse event considered to be possibly, probably or definitely related to the study drug by the study Medical Monitor, then the study must be stopped and the Institutional Review Boards, and FDA's Division of Antiviral Drug Products will be notified. All safety and activity data will be submitted to the FDA in a timely manner.

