11.2. Subject Discontinuation

Treatment will be discontinued for individual subjects for the following reasons:

1. An allergic reaction occurs or is suspected.
2. Medical conditions that may require study discontinuation in the Investigator's judgment.
3. Subject desire to discontinue participation.

In the case of an allergic reaction or other medical condition requiring subject discontinuation, appropriate treatment will be instituted by the Investigator.

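### Protocol 10.4 ends study participation, not only study drug, after a severe adverse reaction, so some non-responders are censored early for a possibly drug-related reason; the expected effect is small and the fix is cheap

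*Protocol*

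**What the plan says.** Four Protocol sections deal with a subject who stops or misses study drug.

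- **10.4**, severe adverse reaction during therapy: "the study medication should be discontinued, and the subject should be withdrawn from the study". These are two separate actions.
- **10.2**, all moderate and severe adverse events: the investigator judges "whether they warrant the subject to be discontinued from the study".
- **9.5**, missed doses: "Non-compliance will not be cause for discontinuation of subject participation in the study".
- **11.2**, headed Subject Discontinuation: it opens with "Treatment will be discontinued for individual subjects for the following reasons", but its second reason speaks of study discontinuation, and 5.9 refers to it for taking a subject out of the study. It mixes the two ideas.

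Some follow-up remains after a 10.4 withdrawal. Section 5.9 gives one exit evaluation: "All subjects discontinued from the study before Day 7 will be evaluated at study discontinuation using the procedures described above for Day 7". Section 10 adds "All adverse events must be followed until their resolution or stabilization even beyond the planned study period", and 10.2 says that "relevant clinical assessments and laboratory tests will be repeated as clinically indicated until final resolution or stabilization" of the event. Neither section provides for further diaries or the Day 22 visit.

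In the analysis the subject stays in the ITTI population. A response before exit counts as an event, and so does meeting the criteria at the last diary without symptom relief medication (SAP 11.2.2). Otherwise the subject is censored at the last diary, for the primary endpoint (Protocol 8.4.1, SAP 11.2.2) and for the key secondary endpoint (SAP 11.4.1). A sensitivity analysis assigns 21 days, or 504 hours, to subjects who leave without a response (Protocol 8.4.1, SAP 11.3.1). It covers the primary endpoint only.

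**The concern.** Stopping the drug protects the subject. Leaving the study adds no protection from further exposure, and it ends the diary that carries both the FLU-PRO items and the activity score. The same severe event can also be handled under 10.4, where exit is directed, or under 10.2, where it is a judgment.

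The stratified Gehan-Wilcoxon tests treat censoring as unrelated to outcome. Here the trigger is an adverse reaction, which may be caused by the drug. The documents give no severe-reaction rate by arm, so equal loss in both arms is an assumption. Protocol 3 reports more diarrhea of any grade on nitazoxanide (8.1% against 5.8%), and Appendix II grades six or more watery stools as severe. If those who leave are slow recoverers, and more of them are on nitazoxanide, censoring drops unfavourable outcomes from the active arm. New complications after exit could also be missed, although Protocol 3 already expects too few to show a difference.

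**Working it through.** **The plan's own figure.** Protocol 8.1 inflates 530 for 12% incomplete data. 530 / 0.88 = 602.3, so 603, against 600 stated; 600 × 0.88 = 528. The allowance reproduces. The 90% power cannot be checked because the input curves are a figure that is not shown. Nothing below depends on it.

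**Diaries lost.** Diaries run through Day 21 (Protocol 5.10) and the trigger falls on Days 1 to 5: 21 − 5 = 16 up to 21 − 1 = 20 entries.

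**Subjects affected.** Protocol 1.2.6 reports that under 1% stopped therapy for an adverse event in earlier trials. I use 1% as an assumption, not as a bound.

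- 0.01 × 600 = 6; 0.01 × 700 = 7.
- Incomplete-data allowance at 700: 0.12 × 700 = 84, and 7 / 84 = 8.3%.
- Splitting 7 by the diarrhea rates: 7 × 8.1 / 13.9 = 4.1 on nitazoxanide and 2.9 on placebo.

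The only ceiling in the plan is the stopping rule in 11.1, which concerns related events: "If greater than 5% of the subjects have at least one Grade 3 or Grade 4 adverse event". Spread evenly over infected subjects, that is 0.05 × 700 = 35 (20.4 and 14.6 on the same split), or 0.05 × 350 = 17.5, so 18, in one arm.

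**Effect on the test with no drug effect.** Simulation, 60,000 runs, 350 per arm, unstratified Gehan-Wilcoxon. Assumptions: exponential times with median 302 h in both arms (placebo, Protocol Table 7), daily grid, censoring at 504 h, withdrawal on Days 1 to 5. The standard error is about 0.06 points on a 2.4% tail.

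| Withdrawn, NTZ vs placebo | Who leaves | NTZ-favouring tail | Two-sided | Mean Z |
|---|---|---|---|---|
| none | – | 2.36% | 4.74% | 0.00 |
| 4 vs 0 | random | 2.46% | 5.05% | 0.00 |
| 20 vs 15 | random | 2.39% | 4.81% | 0.00 |
| 4 vs 3 | slowest | 2.82% | 5.24% | +0.04 |
| 4 vs 0 | slowest | 3.57% | 5.40% | +0.15 |
| 7 vs 0 | slowest | 4.49% | 5.95% | +0.26 |
| 20 vs 15 | slowest | 4.24% | 6.14% | +0.18 |
| 18 vs 0 | slowest | 10.08% | 10.59% | +0.66 |

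A shorter repeat (8,000 runs) gave 2.5% for 4 vs 3 slowest, so that case is close to no change.

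**With the planned 21-day analysis.** Hour 504 falls on Day 22 at the clock time of the first dose, after the Day 21 evening diary. Assigning 504 h therefore ranks withdrawn subjects behind everyone followed to Day 21. On that ordering the worst-case shift returns to about 0.00, for 4 vs 0 and for 18 vs 0. This is as expected: under the assumed curve, exp(−ln 2 × 504 / 302) = 31% of subjects are unrecovered at 504 h, so the slowest few are essentially all in that group. If completers are instead censored at exactly 504 h, only about 40% of the shift is removed. When 4 vs 0 leave at random, the same analysis gives about −0.10 in Z, against nitazoxanide.

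**Second set of assumptions, with a drug effect.** 300 per arm, 1,500 runs, Weibull shape 1.5, placebo median 192 h, nitazoxanide 33 h shorter, withdrawal at 24 to 120 h. Continued follow-up against censoring at exit:

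- 3 vs 0, same prognosis: power 83.7% vs 83.8%; mean Z 2.95 in both.
- 3 vs 0, recovering twice as slowly: power 81.3% vs 83.5%; mean Z 2.88 vs 2.95.
- 15 vs 0 (5% of one arm), twice as slowly: power 69.1% vs 80.3%; mean Z 2.47 vs 2.81.

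**The case against.** The strongest reply is that this is a cautious safety rule for a rare event, and that the plan already checks its consequence. Much of that stands.

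- Section 10.4 covers a narrower case than 10.2 and is worded as what should happen. A specific rule beside a general one is not a contradiction, and 9.5 concerns missed doses rather than safety. What remains is that 10.4 directs exit where 10.2 would weigh it, and 9.5 shows that follow-up off drug is already accepted.
- A reader might infer that 11.2 contradicts 10.4 by stopping treatment only. Its text does not support that, because it mixes treatment and study exit.
- A reader might infer a serious false-positive risk from the 7 vs 0 or 18 vs 0 rows. The documents do not support this. The rows need all losses in one arm and the slowest recoverers picked out by Day 5, and nothing in the documents shows either. The 5% figure is a stopping threshold over all enrolled subjects (up to 1,750), not an expected rate in infected ones.
- Any-grade diarrhea is a weak proxy for severe reactions of all kinds. In Protocol Table 9, nausea (3.9% vs 5.3%) and vomiting (2.5% vs 2.7%) were less frequent on nitazoxanide alone than on placebo.
- The 21-day analysis largely answers the worst case for the primary endpoint. It does so with an assigned value, which is too harsh if withdrawal is unrelated to recovery, and it does not extend to the key secondary endpoint.

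**Conclusion.** The point holds as a small, avoidable weakness. Section 10.4 gives up primary and key secondary data that could still be collected, and censors non-responders for a possibly drug-related reason.

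At the historical rate this concerns about 6 to 7 infected subjects, fewer if some have already responded. There is no bias if withdrawal is unrelated to recovery. If the slowest recoverers leave, the shift is +0.04 (4 vs 3) to +0.15 (4 vs 0) in Z, favouring nitazoxanide, before the 21-day analysis is applied. No conclusion is likely to turn on this.

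The figures rest on the under-1% rate carrying over, on the assumed recovery curves, and on an unstratified test in place of the stratified one. The neutralising effect of the 21-day analysis also rests on diaries ending on Day 21, as in Protocol 5.10 and SAP 8.2. A footnote to the schedule of assessments carries them to Day 22 (+3), and the ordering would then not be guaranteed.

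**What to change.** Change 10.4 so that a severe adverse reaction stops study drug only. Align 10.2 and 11.2 with it, stating that stopping drug does not by itself end participation and separating reasons for stopping treatment from reasons for leaving the study. State that diaries continue to Day 21 and that the Day 7 and Day 22 visits take place unless consent is withdrawn, and that these data enter the ITTI analyses. Keep the 21-day sensitivity analysis for subjects who do leave.

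The cost is protocol wording plus, at the historical rate, at most 7 × 20 = 140 daily entries in total and the scheduled visits. Protocol 3 puts the average FLU-PRO completion time in an ongoing study below four minutes. Sample size, alpha and the test do not change. The downside is minor burden for a handful of unwell subjects, some of whom may withdraw consent anyway.

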10.5. Medication Errors

A medication error is defined as any preventable event related to dosing instructions, product labeling, or packaging that causes or leads to inappropriate medication use or subject harm while the medication is in the control of the investigative site or subject. Medication errors which result in adverse events should be recorded and reported as adverse events. All other medication errors should be reported to the study Sponsor through the Medical Affairs department within 7 days of identification by the site.

11. DISCONTINUATION

11.1. Study Discontinuation

The study may be discontinued under the following circumstances:

1. The Sponsor reserves the right to discontinue the study at any time.
2. Adverse event listings will be produced for safety monitoring at least once every two weeks during recruitment. The data will be tested to determine if there are greater than 5% of the subjects who have had \geq Grade 3 adverse events considered by the Investigator to be possibly, probably or definitely related to the study drug (defined by the Toxicity Grading Scale Tables provided in [Appendix II](#)).

If greater than 5% of the subjects have at least one Grade 3 or Grade 4 adverse event considered to be possibly, probably or definitely related to the study drug by the study Medical Monitor, then the study must be stopped and the Institutional Review Boards, and FDA's Division of Antiviral Drug Products will be notified. All safety and activity data will be submitted to the FDA in a timely manner.

11.2. Subject Discontinuation

Treatment will be discontinued for individual subjects for the following reasons:

1. An allergic reaction occurs or is suspected.
2. Medical conditions that may require study discontinuation in the Investigator's judgment.
3. Subject desire to discontinue participation.

In the case of an allergic reaction or other medical condition requiring subject discontinuation, appropriate treatment will be instituted by the Investigator.

12. ELECTRONIC DATA COLLECTION (EDC) SYSTEM

An EDC system will be used for this study ([REDACTED]). Prior to study initiation, site staff and authorized Romark personnel will be trained to use this system.

All electronic source forms are to be filled out completely by the examining site staff and reviewed and signed off on by the Investigator(s). Electronic diaries will be completed by the study subjects and reviewed by study personnel and authorized Sponsor representatives.

13. RETENTION OF RECORDS

Essential Documents (EDs) are documents that individually and collectively permit evaluation of the conduct of a trial and quality of the data produced. They demonstrate the compliance of the Investigator, Sponsor, and monitor with the GCP standards and with all applicable regulatory requirements.

In compliance with the ICH/GCP guidelines, the Investigator/institution will maintain all eCRFs and all EDC source forms and source documents that support the data collected from each subject, as well as all study documents as specified in ICH/GCP Section 8, Essential Documents for the Conduct of a Clinical Trial, and all study documents as specified by the applicable regulatory requirement(s). A list of these documents is found in [Appendix III: List of Essential Document for the Investigative Site](#). The Investigator/institution will take measures to prevent accidental or premature destruction of these documents.

Essential documents listed in [Appendix III](#) must be retained for the duration required by applicable regulatory authorities or until the Sponsor informs the Investigator/institution these documents are no longer needed.

If it becomes necessary for the Sponsor or the appropriate regulatory authority to review any documentation relating to this study, the Investigator must permit access to such reports.

The Sponsor is responsible for organizing and maintaining the Trial Master File which is a clear documentation of the course of the study.

14. MONITORING THE STUDY

Monitoring will be conducted by the Sponsor and/or a contract research organization (CRO) according to the Sponsor's standard operating procedures. Site visits will be conducted by the Sponsor at regular intervals to conduct inspections.

Any data transcribed into the EDC system will be 100% source verified.

The Investigator will grant representatives of the Sponsor's clinical operations team and quality team, as well as regulatory agencies and ethical committees access to inspect facilities and records (including subject charts) relevant to this study and agrees to assist the monitors in their activities, if requested.

Given the short duration of this study, the large clinical experience with NTZ, and the population being studied, the data from this study will not be monitored by an independent data monitoring committee.

15. INFORMED CONSENT

Each subject must give written consent according to local requirements after the nature of the study has been fully explained. The informed consent form (ICF) must be signed before performance of any study-related activity. The informed consent form will be approved by both the Sponsor and by the reviewing IRB. They will be in accordance with principles that originated in the [Declaration of Helsinki](#), current ICH and GCP guidelines, applicable regulatory requirements, and Sponsor policy.

Before enrollment in the study, the Investigator or an authorized member of the investigational staff must explain to potential subjects the aims, methods, reasonably anticipated benefits, and potential hazards of the study, and any discomfort participation in the study may entail. Subjects will be informed that their participation is voluntary and that they may withdraw consent to participate at any time. They will be informed that choosing not to participate will not affect the care he/she will receive. Finally, they will be told that the Investigator will maintain a subject identification register for the purposes of long-term follow-up if needed and that their records may be accessed by health authorities and authorized Sponsor staff without violating the confidentiality of the subject, to the extent permitted by the applicable law(s) or regulations. By signing the ICF the subject is authorizing such access, and agrees to allow his or her study physician to re-contact the subject for the purpose of obtaining consent for additional safety evaluations, if needed.

The subject will be given sufficient time to read the ICF and the opportunity to ask questions. After this explanation and before entry into the study, consent should be appropriately recorded by means of the subject's personally dated signature. After having obtained the consent, a copy of the ICF must be given to the subject.

If the subject is unable to read or write, an impartial witness should be present for the entire informed consent process (which includes reading and explaining all written information) and should personally date and sign the ICF after the oral consent of the subject is obtained, if permitted by local law.

Assent from any minor (≤ 18 years of age or as local regulations apply) enrolled into the study will be obtained along with documented consent from their parent/legal guardian to allow the minor to participate in the study. The assent and consent forms must be signed prior to the performance of any study related activity.

Signed ICFs must remain in the subject's file(s) and be available for verification by representatives of Romark, the IRB, and FDA/relevant regulatory agencies at any time.

